#### 7.0 TRIAL PROCEDURES

#### 7.1 **Trial Procedures**

The Trial Flow Chart - Section 6.0 summarizes the trial procedures to be performed at each visit. Individual trial procedures are described in detail below. It may be necessary to perform these procedures at unscheduled time points if deemed clinically necessary by the investigator.

Furthermore, additional evaluations/testing may be deemed necessary by Sanford Research and/or Merck for reasons related to subject safety. In some cases, such evaluation/testing may be potentially sensitive in nature (e.g., HIV, Hepatitis C, etc.), and thus local regulations may require that additional informed consent be obtained from the subject. In these cases, such evaluations/testing will be performed in accordance with those regulations.

#### 7.1.1 Administrative Procedures

#### 7.1.1.1 Informed Consent

The Investigator must obtain documented consent from each potential subject prior to participating in a clinical trial.

#### 7.1.1.1.1 General Informed Consent

Consent must be documented by the subject's dated signature on a consent form along with the dated signature of the person conducting the consent discussion.

A copy of the signed and dated consent form should be given to the subject before participation in the trial.

The initial informed consent form, any subsequent revised written informed consent form and any written information provided to the subject must receive the IRB/ERC's approval/favorable opinion in advance of use. The subject should be informed in a timely manner if new information becomes available that may be relevant to the subject's willingness to continue participation in the trial. The informed consent will adhere to IRB/ERC requirements, applicable laws, regulations, and Sanford Research requirements.

#### 7.1.1.2 Inclusion/Exclusion Criteria

All inclusion and exclusion criteria will be reviewed by the investigator or qualified designee to ensure that the subject qualifies for the trial.

#### 7.1.1.3 Medical History

A medical history will be obtained by the investigator or qualified designee. Medical history will include all active conditions, and any condition diagnosed within the prior 10 years that are considered clinically significant by the Investigator. Details regarding the disease for

which the subject has enrolled in this study will be recorded separately and not listed as medical history.

#### 7.1.1.4 **Prior and Concomitant Medications Review**

#### 7.1.1.4.1 Prior Medications

The investigator or qualified designee will review prior medication use, including any protocol-specified washout requirement, and record prior medication taken by the subject within 28 days before starting the trial. Treatment for the disease for which the subject has enrolled in this study will be recorded separately and not listed as a prior medication.

#### 7.1.1.4.2 Concomitant Medications

The investigator or qualified designee will record medication, if any, taken by the subject during the trial. All medications related to reportable SAEs and ECIs should be recorded as defined in Section 7.2.

#### 7.1.1.5 **Disease Details and Treatments**

#### 7.1.1.5.1 Disease Details

The investigator or qualified designee will obtain prior and current details regarding disease status.

#### 7.1.1.5.2 **Prior Treatment Details**

The investigator or qualified designee will review all prior cancer treatments including systemic treatments, radiation and surgeries.

#### 7.1.1.5.3 Subsequent Anti-Cancer Therapy Status

The investigator or qualified designee will review all new anti-neoplastic therapy initiated after the last dose of trial treatment. If a subject initiates a new anti-cancer therapy within 30 days after the last dose of trial treatment, the 30-day Safety Follow-up visit must occur before the first dose of the new therapy. Once new anti-cancer therapy has been initiated, the subject will move into survival follow-up.

#### 7.1.1.6 Assignment of Screening Number

Consented subjects will be assigned a screening number. Specific details on the screening visit requirements (screening/rescreening) are provided in Section 7.1.5.1.

#### 7.1.1.7 Assignment of Study Subject Number

Subjects will be assigned a subject study number at enrollment. This number will be unique to this subject.

#### 7.1.1.8 **Trial Compliance (Medication/Diet/Activity/Other)**

Interruptions from the protocol specified treatment plan for >1 week require consultation with the principal investigator. Written documentation of the collaborative decision is required.

Missed doses of the study drug, pembrolizumab, will be monitored and tracked. This will be analyzed as part of the safety and tolerability portion of the analysis.

#### 7.1.2 Clinical Procedures/Assessments

#### 7.1.2.1 Adverse Event (AE) Monitoring

The investigator or qualified designee will assess each subject to evaluate for potential new or worsening AEs as specified in the Trial Flow Chart and more frequently if clinically indicated. Adverse experiences will be graded and recorded throughout the study according to NCI CTCAE Version 4.0 (see Section 11.2). Toxicities will be characterized in terms regarding seriousness, causality/attribution, toxicity grading, and action taken with regard to trial treatment.

AEs should be assessed up to 30 days following cessation of treatment and followed for 90 days for SAEs, even if the patient transitions to follow-up during this time. Once a subject transitions to follow-up all documented AEs will be followed until resolution or to a new baseline as determined by the treating investigator. Only new AEs that could be considered an ECI or irAR will be documented and followed while in follow-up.

All AEs of unknown etiology associated with pembrolizumab exposure should be evaluated to determine if it is possibly an event of clinical interest (ECI) of a potentially immunologic etiology (termed immune-related adverse events, or irAEs); see the separate ECI guidance document regarding the identification, evaluation and management of potential irAEs.

Please refer to section 7.2 for detailed information regarding the assessment and recording of AEs.

#### 7.1.2.2 Full Physical Exam

The investigator or qualified designee will perform a complete physical exam during the screening period. Clinically significant abnormal findings should be recorded as medical history.

#### 7.1.2.3 Directed Physical Exam

For cycles that do not require a full physical exam per the Trial Flow Chart, the investigator or qualified designee will perform a directed physical exam as clinically indicated prior to trial treatment administration.

#### 7.1.2.4 Vital Signs

The investigator or qualified designee will take vital signs at screening, prior to the administration of each dose of trial treatment and at treatment discontinuation as specified in the Trial Flow Chart (Section 6.0). Vital signs after Day 150 will be at the discretion of the treating investigator. Vital signs should include temperature, pulse, weight and blood pressure. Height will be measured at screening only.

#### 7.1.2.5 Eastern Cooperative Oncology Group (ECOG) Performance Scale

The investigator or qualified designee will assess ECOG status (see Section 11.1) at screening, prior to the administration of each dose of trial treatment and discontinuation of trial treatment as specified in the Trial Flow Chart.

#### 7.1.2.6 **Tumor Imaging and Assessment of Disease**

#### 7.1.2.6.1 Baseline Tumor Imaging

Initial tumor imaging must be performed within 42 days prior to enrollment. Baseline imaging does not need to have a centralized study review to determine subject eligibility. The baseline imaging scan should be reviewed by each individual site prior to enrollment to confirm measurable disease.

Scans performed as part of routine clinical management are acceptable for use as the screening scan if they are of diagnostic quality and performed within 42 days prior to the enrollment.

The only required imaging modality for the study is a diagnostic quality CT scan of the neck. This should be adequate to fully include the primary tumor and involved locoregional disease. Additional imaging is allowed, but not required for the study. This includes, but is not limited to CT imaging of the head, chest, abdomen, and pelvis, MRI imaging, and FDG-PET imaging.

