#### 3.2 Secondary Objective(s) & Hypothesis (es)

1. **Objective:** To estimate progression-free survival (PFS), overall survival (OS), the locoregional control rate (LRC), and distant metastases (DM) rate at 1- and 2-years in subjects treated with pembrolizumab given in combination with CRT.

**Hypothesis**: The addition of pembrolizumab to standard CRT will show increased efficacy in terms of key survival endpoints utilized in head and neck cancer.

2. **Objective:** To determine the best overall response rate (ORR) as defined by RECIST 1.1 at treatment end imaging in subjects with Stage III-IVB SCCHN treated with pembrolizumab given in combination with CRT.

**Hypothesis**: The addition of pembrolizumab to standard CRT will show superior ORR compared to historical controls.

4. **Objective:** To estimate the quality of life (QOL) of subjects with Stage III-IVB SCCHN treated with pembrolizumab in combination with CRT during therapy, treatment end, and 1- and 2-years following treatment.

**Hypothesis**: Acute and long-term QOL of participants treated with the combination of pembrolizumab and low dose weekly cisplatin and radiation will be superior to historical controls.

5. **Objective:** To correlate ORR, PFS, OS, LRC, and DM with tumor PD-L1 expression in subjects with Stage III-IVB SCCHN treated with pembrolizumab in combination with CRT.

**Hypothesis**: High PD-L1 expression has correlated with responses in the metastatic setting and will correlate with key disease response and survival outcomes in the curative intent setting.

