# 6.3 Follow-up

		Months Following Study Treatment End (after day 150 imaging)								
Follow-up Month	Follow up visit 1 (90 days from Day 150)	Follow up visit 2 (90 days from FU-V1)	Follow up visit 3 (180 days from FU-V2)	Follow up visit 4 (180 days from FU-V3)	Follow up visit 5 (180 days from FU-V4)	Follow up visit 6 (352 days from FU-V5)	Follow up visit 7 (352 days from FU-V6)	Follow up visit 8 (352 days from FU-V7)	Study End	
Scheduling Window	+/- 14 days	+/- 30 days	+/- 30 days	+/- 30 days	+/- 30 days	+/- 30 days	+/- 30 days	+/- 30 days		
Administrative Procedures									]	
Subsequent antineoplastic therapy status	x	X	X	X	X	x	X	X		
Survival Status 	X	x	x	x	x	x	x	X	-	
Clinical Procedures and Asses	sments				I		I		1	
Adverse Events 	x	X	X	X	x	x	x	x	-	
Directed Physical Exam	x	x	X	X	x	X	x	x		
Vitals and Weight (optional)	x	x	X	X	x	X	x	x		
ECOG PS(optional)	X	x	x	X	X	X	X	X		

	Months Following Study Treatment End (after day 150 imaging)								
Follow-up Month	Follow up visit 1 (90 days from Day 150)	Follow up visit 2 (90 days from FU-V1)	Follow up visit 3 (180 days from FU-V2)	Follow up visit 4 (180 days from FU-V3)	Follow up visit 5 (180 days from FU-V4)	Follow up visit 6 (352 days from FU-V5)	Follow up visit 7 (352 days from FU-V6)	Follow up visit 8 (352 days from FU-V7)	Study End
Scheduling Window	+/- 14 days	+/- 30 days	+/- 30 days	+/- 30 days	+/- 30 days	+/- 30 days	+/- 30 days	+/- 30 days	
Laboratory Procedures/Assess	nents (local labor	atory testing):							
CBC with differential	x	x	x	x	x	X	x	x	-
Serum Chemistry Panel 	X	x	x	X	x	X	x	x	-
T3, FT4, TSH		x	X	X	X	X	x	x	
Imaging									-
Tumor Imaging (CT neck)	X	x	x		x	x	x	x	-
Correlative Study Procedures	 	I	 						
Blood for correlative studies 			x						
Patient Reported Outcomes (PI	RO)				 			 	
FACT H&N 			x		x				

1. Treatment day 1 coincides with the first day of radiation therapy. Any treatment days before will be denoted with a preceding (-) symbol.

2. The window for each visit is outlined as above. If a treatment is delayed, the following treatment must occur with the same delay. Additional treatment delay can occur with the specified scheduling window. If treatment is delayed beyond that window, treatment for that scheduled course must be held. Treatment can be resumed for the next scheduled treatment day.

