3. Radiation occurs continuously throughout therapy until the total of 35 fractions has been completed. Therefore, the dates listed may not always have radiation treatment on that date. All radiation should be completed by day 52.

4. For women of reproductive potential, a urine pregnancy test will be performed within 72 hours prior to the first dose of trial treatment. If urine pregnancy tests cannot be confirmed as negative, a serum pregnancy test, performed by the local lab, will be required. Pregnancy tests (serum and/or urine tests) should be repeated if required by local guidelines.

5. The serum chemistry panel includes tests listed in Section 7.1.3, Table 5(Albumin, AST, ALT, Alkaline phosphatase, Total Bilirubin (and direct bilirubin if elevated), Total Protein, CO2, Calcium, Chloride, Glucose, Potassium, Sodium, Creatinine, and BUN).

6. p16 immunohistochemistry status is required on all patients. This can be performed by the local laboratory sites. High risk HPV DNA testing at an outside lab can be performed if p16 staining is indeterminate or not able to be obtained. See section 5.1.2 for details.

7. Tumor tissue for biomarker analysis from an archival tissue sample or fresh biopsy must be provided for enrollment. Detailed instructions for tissue collection, processing and shipment are included in the procedures manual.

10. Blood for correlative flow cytometry studies will be drawn throughout treatment. On days with corresponding treatment, this should be drawn within 24 hours prior to treatment with pembrolizumab or chemotherapy. Procedures for sample collection, processing, and shipment are included in the procedures manual.

11. Patient reported outcomes (PRO) will be assessed using the FACT H&N form (see Appendix 11.8). PRO forms must be completed on paper or electronically by subjects prior to all other study procedures for that date. Patients who go off-treatment but continue follow up should be encouraged to complete PRO at the times outlined in the calendar.

12. Tumor imaging will be completed at baseline and after treatment has finished, on approximately day 150-157. Baseline imaging must be completed within 42 days of enrollment. Required imaging for the study protocol is diagnostic quality imaging of the neck. Additional imaging techniques can be utilized (i.e. MRI, FDG-PET, etc.), but are not required for study procedures.

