#### 7.1.2.6.2 Tumor Imaging During Trial

The first imaging assessment should be performed at approximately **100 days after completion of radiation therapy**. For the purposes of this study, this is considered the "treatment end" imaging study. This will be approximately day 150 from the first dose of radiation. Due to treatment variations and delays, this may be delayed by up to 14 days.

Follow-up imaging will occur at scheduled intervals outlined on the Flow Chart. At 1 year following completion of the study treatment PET/CT imaging is not required, but is suggested

and is allowed so long as diagnostic quality CT images are included. Diagnostic quality imaging of the primary tumor site (CT scan of the neck) should be performed annually thereafter for up to 5 years. Images will be reviewed by the central radiologist at the end of the study to confirm disease response for purposes of study evaluation.

Additional imaging should be performed per clinical guidelines and is not required the study. Patients with clinical signs and symptoms of progression should have follow-up imaging as deemed clinically necessary. If this occurs during the study period, it should be reported to the study.

During the follow up period, if an instance occurs where the participants insurance will not approve a diagnostic CT scan a clinical evaluation will be used. No protocol deviation is needed but the insurance denial must be documented on the tumor assessment source documents.

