#### 8.4 Analysis Endpoints

#### 8.4.1 **Efficacy Endpoints**

Radiographic Complete response (rCR) rate: proportion of subjects in the analysis population who have a complete response on RECIST 1.1 imaging at treatment end.

PET NPV rate: proportion of subjects in the analysis population who are considered to have NPV based on Hopkins Criteria scoring at treatment end.

Pathologic complete response (pCR) rate: proportion of subjects in the analysis population who have stable disease (SD) or partial response (PR) on RECIST 1.1 imaging at treatment end, who undergo salvage surgical resection and have a complete response determined on histologic evaluation.

Overall Complete Response (CR) rate: this is a composite proportion of subjects in the analysis population with a rCR, PET NPV, and pCR. This is the primary measure of efficacy for the study.

Overall Response Rate (ORR): proportion of subjects in the analysis population who have complete response (CR) or partial response (PR) based on RECIST 1.1 imaging at treatment end.

Progression-Free Survival (PFS): time from Day -7 treatment administration to the first documented disease progression or death.

Overall Survival (OS): time from Day -7 treatment administration to death due to any cause.

Locoregional Control (LRC): time from day -7 treatment to date of local or regional relapse within the primary radiation treatment field (relapse in the head or neck region, excluding CNS recurrence).

Rate of Distant Metastases (DM): proportion of subjects in the analysis population who develop distant recurrence, as defined by recurrence outside of the primary radiation treatment field (head and neck region).

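### No required scan covers distant sites and DM-free status is not defined, so the 1- and 2-year distant metastasis rate depends on optional imaging and its bias could run either way

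*Combined protocol and SAP*

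**What the plan says.** Section 3.2, objective 1, is to estimate the "distant metastases (DM) rate at 1- and 2-years in subjects treated with pembrolizumab" plus chemoradiotherapy. Section 8.4.1 defines DM as the proportion of patients with recurrence outside the irradiated head and neck region.

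On imaging:

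- **Baseline (7.1.2.6.1):** "The only required imaging modality for the study is a diagnostic quality CT scan of the neck". Chest, abdomen, pelvis and PET imaging come under "Additional imaging is allowed, but not required for the study".
- **Baseline and treatment end (flow chart, footnote 12):** "Required imaging for the study protocol is diagnostic quality imaging of the neck". Footnote 14 makes PET optional.
- **Follow-up (6.3):** the imaging row names CT neck only, at visits 1, 2, 3, 5, 6, 7 and 8.
- **During the trial (7.1.2.6.2):** PET/CT is suggested at 1 year. Otherwise, "Additional imaging should be performed per clinical guidelines and is not required the study". Patients with signs or symptoms of progression should be imaged and this reported to the study. The section is silent on reporting other routine imaging. If insurance refuses a follow-up CT, clinical evaluation replaces it.

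Table 7 analyses DM in the Full Analysis Set as a binomial proportion with a Clopper-Pearson interval, and treats missing DM data as disease not controlled. Section 2.1 instead speaks of cumulative incidence. Section 4.2.3.1 plans to compare the secondary endpoints with historical data and allows them to weigh in the decision to go further.

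**The concern.** The endpoint event occurs outside the neck, and the scans that the plan requires show the neck. A site can follow the protocol fully and hold no image, at 1 or 2 years, of the places where DM would appear. Detection of silent DM then varies with site habit, insurance and symptoms, and detected cases may be dated late.

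The same gap reaches progression-free survival. Table 7 bases it on independent radiology review, which cannot see distant progression in a patient who has only neck images.

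What is at stake is the historical comparison in Section 4.2.3.1. In a single-arm trial, a DM rate that looks low may reflect less looking, and one that looks high may reflect the missing-data rule. As written, the plan would not let a reader tell these apart from a treatment effect, because it does not clearly collect negative routine body scans.

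**Working it through.** The plan gives no expected DM rate, precision or power for DM, so there is no figure to reproduce. The check is textual, followed by an illustration on assumed inputs.

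**1. Required scans at the landmarks.** Summing the intervals in Section 6.3, follow-up visits fall 90, 180, 360, 540, 720, 1072, 1424 and 1776 days after day 150. The visits nearest 1 and 2 years after treatment end are visit 3 (day 360) and visit 5 (day 720). Both require a neck CT only. PET/CT is suggested at the first landmark, and nothing beyond the neck is named for the second. Appendix 11.4 gives a different, denser follow-up interval for patients who stop treatment early. It names no body region and does not match the flow chart.

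**2. Inputs for the illustration.** N = 57 is planned enrolment; the Full Analysis Set may be smaller. The true DM rate t = 10%, 15% or 20% and the share detected s = 75% or 50% are assumptions. The share missing m is varied.

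**3. Nobody missing.** Observed rate = t × s. For example, 0.15 × 0.75 = 11.25% and 0.15 × 0.50 = 7.5%. For reference, full detection at t = 15% gives about 9/57 (95% CI 7.5% to 27.9%).

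**4. Table 7 rule applied.** If missing patients count as events, observed rate = m + (1 − m) × t × s. This equals t when m = t(1 − s)/(1 − ts). For t = 0.15:

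- s = 0.75: 0.0375/0.8875 = 4.2%
- s = 0.50: 0.075/0.925 = 8.1%

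| t | s | Observed, m = 0 | Count of 57 (95% CI) | Break-even m | Observed, m = 10% | Observed, m = 20% |
|---|---|---|---|---|---|---|
| 10% | 75% | 7.5% | 4 (1.9–17.0%) | 2.7% | 16.8% | 26.0% |
| 10% | 50% | 5.0% | 3 (1.1–14.6%) | 5.3% | 14.5% | 24.0% |
| 15% | 75% | 11.25% | 6 (4.0–21.5%) | 4.2% | 20.1% | 29.0% |
| 15% | 50% | 7.5% | 4 (1.9–17.0%) | 8.1% | 16.8% | 26.0% |
| 20% | 75% | 15.0% | 9 (7.5–27.9%) | 5.9% | 23.5% | 32.0% |
| 20% | 50% | 10.0% | 6 (4.0–21.5%) | 11.1% | 19.0% | 28.0% |

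Below break-even the DM rate is understated; above it, overstated. Across the grid, break-even is 2.7% to 11.1% missing, or about 2 to 6 of 57 patients (0.027 × 57 = 1.5; 0.111 × 57 = 6.3).

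**5. The undefined classification.** Suppose 10% to 30% of patients have no body imaging (assumption). That is 0.10 × 57 = 5.7 to 0.30 × 57 = 17.1, about 6 to 17 patients. Reading them all as DM-free or all as missing moves the reported rate by up to 10 to 30 percentage points.

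**The case against.** The schedule leaves real routes to detection. PET/CT is suggested at 1 year, which is a DM landmark. Guideline imaging is expected in care, symptomatic patients should be imaged and reported, and directed physical examination, survival status and later anticancer therapy are recorded at all eight follow-up visits. A reader might infer that the trial cannot detect DM. The documents do not support that: detection is unsystematic, not impossible.

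A reader might also infer that DM will be understated. That follows only if patients with neck-only imaging are treated as DM-free. The Table 7 rule pushes the other way, and a few missing patients are enough to reverse the sign.

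Nor can one infer that absence of metastases goes unassessed at entry. Clinical stage III to IVB must be established and stage IVC is excluded. The plan simply names no image to support this.

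It is also fair that DM is secondary, is given an interval without a formal test, and may inform the go-forward decision only if the analysis is statistically sound. How the historical studies looked for DM is not stated, so a bias in that comparison cannot be demonstrated from the documents.

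All of this limits the strength of the claim. It does not remove the two gaps: no required scan covers distant sites, and DM-free status has no definition.

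**Conclusion.** The point holds as a fault of ascertainment and definition. The 1- and 2-year DM rate depends on imaging that the plan neither requires nor clearly collects, and silent DM may be missed or dated late. The net direction of bias for DM is unknown.

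With nobody missing, the assumed ranges (true rate 10% to 20%, 50% to 75% detected) give an understatement of 2.5 to 10 points (0.10 × 0.25 to 0.20 × 0.50). This is an illustration only, since it leaves out the missing-data rule. The undefined status of patients without body imaging could matter more: up to 10 to 30 points if 10% to 30% of patients are in that position.

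For progression-free survival, Table 7 censors at the last assessment, so there is no adverse missing-data rule to offset late or missed distant progression. The documents give no basis for a size.

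The primary endpoint analysis and the sample size do not turn on this point. It should be repaired because the repair is cheap and changes what can be concluded about DM.

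**What to change.** No scan needs to be added.

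1. On the tumour assessment form, record the date and body region of every chest, PET or whole-body image done in routine care, negative or positive, including the staging image that supports absence of metastases at entry. For patients already treated, take this from the medical record.
2. In Section 8.4.1 and Table 7, name the endpoint *clinically detected DM* and state when a patient without body imaging counts as missing. Reconcile this with the existing missing-data rule, and settle whether the measure is a proportion (8.4.1, Table 7) or a cumulative incidence (2.1).
3. Report how many patients had chest-covering imaging by 1 and by 2 years, with a sensitivity analysis that reclassifies those who did not.
4. In Section 4.2.3.1, exclude DM from the historical superiority comparison and from the go-forward decision.

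Censoring at the last chest-covering image should not be the main analysis. If imaging is prompted by symptoms, it removes well patients early and keeps the events. For example, take 6 detected events among 57, with 30 of the other 51 never imaged and censored at the start. The estimate is then about 6/27 = 22%, against 6/57 = 10.5% detected and an assumed true rate of 15%. It would also replace the Table 7 method and contradict the label of clinically detected DM.

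The cost is one extra case report form entry, some SAP wording and a weaker claim about DM.
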